Page 10 of 31 Version Date: 12/2/2021

complete the study.

6. Study Timelines

Procedures and Timing: Data will be collected for all subjects at five time points: T1 baseline (36.0-37.6 weeks), T2 (on labor admission), T3 (postpartum day 0-14), T4 (2 weeks postpartum), and T5 (6 weeks postpartum) as indicated in the table below.

Following informed consent, participants will have their first study visit at 36.0-37.6 weeks gestation (T1), during which baseline data will be collected and each subject will complete several brief questionnaires. Participants will be randomized into intervention group or routine care. The research staff member will sequentially distribute one prelabeled bottle of 30 probiotic capsules to the intervention group at time of enrollment. The bottle number will be used as the subject's number for the remainder of the study. Subjects in the control group will not receive any capsules and will be advised to continue their routine prenatal self-care. All subjects in the intervention group will be instructed to keep the study bottle in the refrigerator and to take one capsule per day until they give birth and to bring the bottle with them to the hospital at the time of labor. The PI, co-investigators, research staff, prenatal providers, and the subjects will not be blinded to group assignment.

The GBS vaginal to rectal swab collection procedure will be repeated for the both the intervention and routine care groups at T2 on labor admission. All participants will receive routine IAP per protocol as per CDC guidelines. At T3, the research staff will complete data collection with every participant during postpartum days 0-14; this will involve counting any remaining capsules in the study bottle, administering the study questionnaires, providing each subject with the first thank you merchandise card, and conducting a record review to document birth characteristics and IAP treatment. Adverse events will be solicited at each prenatal visit and via formal questionnaire for participants at T3-T5. Adverse events will be solicited at each prenatal visit and via formal questionnaire at T4-T5 for the newborn(s). A second merchandise card will be provided at T5.

Page 11 of 31 Version Date: 12/2/2021

Summary of Study Data Collection, Variables, Measures, and Timing

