Outcome Variables	Study Data Collection Research staff will document data from all measures on the Summary Data Collection Form.	T1 Baseline 36-37 ^{6/7}	T2 Admission to L&D	T3 Postpartum Day 0-14	T4 2 weeks postpartum	T5 6 weeks postpartum
	Procedures					
Qualitative GBS Colonization (+ or -)	Vaginal-rectal GBS swab.		X			
Intervention Adherence [Probiotic group only]	Final Capsule Count			X		
Maternal GI Symptoms	Antepartum Gastrointestinal Symptom Assessment (AP-GI-SA-10)	Х		Х		

Version Date: 12/2/2021

Adverse Events	Adverse Event Solicitation and Documentation Form [Prenatal providers will also solicit for adverse events at all prenatal visits between study visits]		X	X	X
Demo- graphics	Demographic Questionnaire	X			
Lifestyle practices: sexual, hygiene, diet	Questionnaire for Participants	X	X		
Future Feasibility Form					X

Version Date: 12/2/2021

Timeline for Completion of the Project

Timeline for Completion	on of the froject
June 2020	-IRB submission -Planning for meetings with division partners (nursing, medical assistants, midwives, OBs, lab) -Create recruitment tools, handouts, posters -Complete translation of all study materials into Spanish -Upload all final questionnaires into the UNM REDCap system, study projectEstablish safe storage procedures for probiotics prior to distribution to participants -Request probiotic shipment from Florajen
July/August 2020	-Work with research staff and clinical partners on protocols for the 2nd GBS swab collection at T2 -Establish protocols for testing and billing of T2 study swabs with UNM Tricore lab -Receive probiotics from Florajen -Orient research staff to project & create parameters for EHR use for tracking patients -Present study at division meetings of partners (residents, clinic staff, faculty, L&D staff, lab) -Receive iPads from Marquette and add data collection forms to the UNM REDCap system.
September 2020	Start recruitment and data collection
April 2021	End recruitment
May 2021	-Final data collection -Begin data analysis in collaboration with Marquette University
May-September 2021	-Data Analysis -Submit for poster presentation at professional conference(s)
Fall 2021	-Grand Rounds Presentation -Development of poster presentation -Write a paper and submit for publication in peer reviewed journal

7. Study Endpoints

Our primary outcome variable is qualitative GBS colonization (positive versus negative), at the time of labor admission.

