Participant flow through the study: Healthy adult pregnant women, who are GBS positive, at \geq 36 weeks gestation, will be introduced to the study. If they express an interest in the study, the research coordinator will conduct a prenatal chart review after their GBS swab result has returned and review study inclusion and exclusion criteria for each interested woman by completing the Prenatal Eligibility Screening Form (PESF). For a woman who is eligible and willing, the research coordinator will complete the informed consent. Participants will provide written or e-signed consent at 36.0 to 37.6 weeks gestation. Consented participants will be randomized to one of two groups, standard of care/control group or the intervention group. Participants in the intervention group will begin taking oral study capsules once daily from time of enrollment/randomization at \geq 36 weeks gestation until the time of birth. The research staff member will sequentially distribute the pre-labeled bottles of study capsules to the intervention group, one bottle of 30 Florajen Digestion probiotic capsules to women in the intervention group at the time of randomization. Because women are seen on a

Page 16 of 31 Version Date: 12/2/2021

weekly basis in late pregnancy, generally we anticipate that participants will receive the probiotic at enrollment; their next regularly scheduled prenatal appointment at approximately 37 weeks gestation. For women who do not attend this appointment in person, research staff can also arrange to meet participants at the prenatal clinic site to initiate the intervention between prenatal appointments. This will be arranged at the woman's convenience. Subjects in the control group will not receive any capsules and will be advised to continue their routine prenatal self-care. All subjects in the intervention group will be instructed to keep the study bottle in the refrigerator and to take one capsule per day until they give birth and to bring the bottle with them to the hospital at the time of labor.

All participants will complete baseline forms: Antepartum Gastrointestinal Symptom Assessment (AP-GI-SA-10), Demographic Questionnaire and the Questionnaire for Participants.

Research coordinators will be filling out a Summary Data Collection Form (SDCF) on all study participants.

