At the time of labor admission to Labor and Delivery, participants will receive a vaginal-rectal GBS swab as a part of the research study. This is not standard of care and thus participants will receive this in addition to the standard of care. The results of the GBS swab will be collected for study purposes only.

All participants regardless of group assignment will receive the usual standard of care for GBS positive status and will be given intrapartum antibiotic prophylaxis (IAP) per protocol during labor.

All participants on postpartum day 0-14, in the hospital will answer these questionnaires: Antepartum Gastrointestinal Symptom Assessment (AP-GI-SA-10), Adverse Event Solicitation and Documentation Form (only for themselves, not their newborn(s)) and Questionnaire for Participants.

*we will not collect Adverse Event Solicitation and Documentation during this study time point because if the information is collected on postpartum day 0, there would be no way of reporting an adverse event for the newborn(s) at this time.

For the intervention group on postpartum day 0-14, study staff will conduct a final capsule count.

All participants at their 2 weeks postpartum visit will have an Adverse Event Solicitation and Documentation Form completed which will also include Adverse Event Solicitation and Documentation for their newborn(s).

Page 17 of 31 Version Date: 12/2/2021

All participants at their 6 weeks postpartum visit will have an Adverse Event Solicitation and Documentation Form & Future Feasibility Form completed which will also include Adverse Event Solicitation and Documentation for their newborn(s).

13. Data Analysis

Demographic characteristics for the full sample and each group will be presented. Logistic regression will be used to identify if the group assignments have relationships to variables such as demographic characteristics, hygiene practices, adherence, and birth characteristics. Logistic regressions test if any of these variables can predict the group that the participants were in. Another advantage of logistic regression is that by adding all the predictors at the same time, we can state the effect of each one controlling for the other predictors, presenting a stronger test of group independence.

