Adverse Event Monitoring: Providers will solicit for adverse events at every patient encounter that are not pregnancy related. [name], CNM, MPH will be alerted if any unexpected adverse event occurs, to determine whether changes in the study protocol (e.g., additional safety measures, change in exclusion criteria) are needed. If any changes to the protocol are needed, [name], CNM, MPH will notify the UNM IRB. Approval of the IRB is necessary prior to introducing any modifications to previously approved protocols that involve human subjects. The PI and the research team will meet monthly to review study progress, including any adverse events. In routine postpartum follow up (T4 and T5), study participants will also be solicited for adverse events. Safety reports will be reviewed monthly by reviewing the data collected on the adverse events questionnaires. The literature will be reviewed on a quarterly basis. One formal interim analysis of efficacy will be performed by a biostatistician at approximately 50% of the total information fraction. A two-sided O'Brien-Fleming boundary will be utilized in conjunction with a Lan-DeMets spending function to assess whether the intervention is showing a much stronger or weaker effect on outcomes than expected. If this occurs, the PIs and research team will give consideration to stopping the trial early. Summary reports of interim analyses will be provided to the funding agency. In the event of suspension or early stopping of the trial, the Human Subjects Protection Program Offices and funding agency grant program official will be promptly notified.

Special Situations: Pregnancy. Marquette University and colleagues have rigorously reviewed the literature on prenatal probiotics in preparation for the proposed study. According to the integrative review of the literature (VandeVusse, et al., 2013; Appendix A.2.), and systematic review and meta-analysis of probiotics against GBS in progress, probiotic agents have been safely used in pregnancy in more than 50 published clinical trials without adverse events to the mother or the fetus. Florjen3 has been used in a pilot study in which 10 pregnant women took this same probiotic once daily orally from 28 weeks through 36 weeks and in a randomized control trial (RCT) conducted under IND#16549 with NIH/NICHD funding 1R21HD095320. No adverse events or negative side effects have been solicited from participants in either study.

15. Withdrawal of Subjects

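### Section 14 restricts provider adverse event solicitation by an undefined pregnancy exclusion that Section 6 does not contain, in the only period when capsules are taken

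*Combined protocol and SAP*

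**What the plan says.** The instruction to prenatal providers appears in three places.

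- Section 14, under adverse event monitoring: "Providers will solicit for adverse events at every patient encounter that are not pregnancy related".
- Section 6, text: "Adverse events will be solicited at each prenatal visit and via formal questionnaire for participants at T3-T5".
- Section 6, data collection table, adverse events row: "Prenatal providers will also solicit for adverse events at all prenatal visits between study visits".

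Only the first carries a restriction. Sections 1 and 7 list adverse events in mother and infant as a secondary outcome and do not exclude events that might be attributed to pregnancy.

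On who does the asking, Section 6 says: "The PI, co-investigators, research staff, prenatal providers, and the subjects will not be blinded to group assignment". On the period of exposure, women in the intervention group are told "to take one capsule per day until they give birth" (Sections 6 and 12). On the first formal form, Section 12 schedules at postpartum day 0-14 the "Adverse Event Solicitation and Documentation Form (only for themselves, not their newborn(s)) and Questionnaire for Participants". On oversight, Section 14 says: "Safety reports will be reviewed monthly by reviewing the data collected on the adverse events questionnaires".

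**The concern.** The product is given in late pregnancy, when many of the events that could happen to a participant might be put down to the pregnancy itself. If pregnancy relatedness decides whether an event is asked about at all, attribution is made before there is a record, and nobody can review it later. Attribution is safer as a judgement on a recorded event.

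Two features of this trial sharpen the point. The judgement would be made by providers who know the group, so it could be made differently for a woman on capsules and a woman on routine care. And two providers who rely on different sections would collect different data for the same secondary outcome. At stake is whether the comparison of antenatal adverse events between arms, and any statement that few or none occurred, can be interpreted.

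**Working it through.** The point involves no sample size, power or rate, and the plan gives no figure to reproduce. The check is a side-by-side reading of every place that describes adverse event capture.

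1. **What the restriction attaches to.** Grammatically, the clause at the end of the Section 14 sentence could qualify either the events or the encounters. If it qualified the encounters, providers would not ask at prenatal visits, which contradicts both statements in Section 6. The workable reading is that it qualifies the events.

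2. **Whether the restriction is defined.** It is not. The documents give no definition of an adverse event, no rule for pregnancy relatedness and no blinded assessor.

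3. **What is scheduled, and when.**

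| Period | Capsules taken | Scheduled adverse event capture | Pregnancy exclusion stated |
|---|---|---|---|
| T1 (36.0-37.6 weeks) to birth | Yes, intervention group | Provider solicitation at prenatal visits | Yes in Section 14; no in Section 6 text and table |
| T3, postpartum day 0-14 | No | Formal form, mother only | No |
| T4, 2 weeks postpartum | No | Formal form, mother and newborn | No |
| T5, 6 weeks postpartum | No | Formal form, mother and newborn | No |

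   The procedures table in Section 22 counts three adverse event forms per participant, which matches T3, T4 and T5. So 0 of 3 formal forms fall in the exposure period, and provider solicitation is the only scheduled prospective capture while capsules are being taken.

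4. **Whether later capture fills the gap.**
   - The T3-T5 forms state no exclusion, so they may pick up antenatal events. But the documents give no look-back period, and the form itself is not among them.
   - The T3 record review covers birth characteristics and antibiotic prophylaxis in both groups. Section 25 lists the birth items: mode of birth, membrane status before the swab, infant weight, length and head circumference, and Apgar scores. None is an antenatal complication such as hypertension, bleeding or infection.
   - Both backups require the woman to be followed to T3. Section 5 allows for 30% dropout, partly because of new risk factors.

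5. **Whether monthly safety review fills the gap.** It works from the questionnaires, and for any one woman these begin after her last capsule. The Section 6 table says that research staff transfer data from all measures to a summary form, but the documents do not say how a provider's prenatal report reaches either that form or the questionnaires.

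Steps 1 to 3 establish a conflict between sections and an undefined entry criterion. Steps 4 and 5 show that the other provisions reduce the gap but do not close it.

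**The case against.** The strongest reply is that one sentence in Section 14 should not be read as governing the plan. Section 6 twice requires unrestricted solicitation, the outcome is defined without the exclusion, and the three postpartum forms carry none. Section 14 itself has an investigator alerted to any unexpected adverse event and has the team review adverse events monthly, neither with a pregnancy exclusion. Women with fever or signs of infection are told to contact the clinic or OB Triage, and membrane status is a listed data item. Section 7 also ties the outcome to the 6-week visit, so antenatal capture might be seen as supplementary. This is, moreover, a feasibility pilot.

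Much of that stands. A reader might infer that the plan as a whole excludes obstetric events. It does not: the exclusion is in Section 14 alone. A reader might also infer that unblinded staff will discard events, or will do so unequally. The documents do not say so; unequal ascertainment is a risk inferred from an undefined judgement in an open-label design.

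Nor should the point be extended to newborns. Newborn questions are left off the T3 form because on day 0 "there would be no way of reporting an adverse event for the newborn(s) at this time". T4 asks them at 2 weeks, when the T3 window closes, and the T3 record review already holds birth size and Apgar scores. The documents therefore do not support saying that women lost after T3 contribute no newborn safety data.

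What the reply does not answer is the conflict itself. Alerts and monthly review depend on an event having come to notice, contact with OB Triage is clinical care rather than study recording, and a form completed after birth with no stated look-back cannot be assumed to recover antenatal events.

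**Conclusion.** The point holds as a conflict between Section 14 and Section 6, joined to an undefined exclusion that unblinded providers would apply. If Section 14 is followed as written, antenatal obstetric events could go unsolicited during exposure, possibly differently by arm, for a stated secondary outcome.

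Its size cannot be put as a number of missed events. The documents give no rate for antenatal events and do not show which section staff would follow, so any count would rest on an outside assumption. What can be stated is the extent in time: from enrollment to birth there is no formal form, and the one scheduled source of adverse event data is described in two incompatible ways.

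The conclusion assumes that the clause in Section 14 qualifies events rather than encounters, and that the postpartum forms do not have an explicit look-back to enrollment. If the forms do have one, the loss would be smaller, but events would be recalled after birth instead of recorded as they occurred. The primary outcome, GBS status on the admission swab, is not affected. The correction is worth making because it is specific, cheap and improves both completeness and comparability of the safety data.

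**What to change.** Reconcile Section 14 with Section 6 by deleting the five-word limiting clause that ends the Section 14 sentence. State one rule for both arms: at every prenatal visit the provider asks about and records all adverse events, whatever the presumed cause. Judge relatedness to pregnancy and relatedness to the product afterwards, in two separate fields.

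The change costs one sentence in the protocol and two fields in the adverse event record. The downside is that more expected pregnancy events will be logged and will need to be classified. No visits or procedures are added, because Section 6 already requires solicitation at each prenatal visit.

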Inclusion of Incarcerated Individuals: Incarcerated individuals will not be included in this study.

Inclusion of Minorities: We anticipate the racial-ethnic composition of the study sample to reflect that of the clinical population. If the proportion of minority women falls significantly below this anticipated number, we will consider targeted recruitment procedures to achieve the projected representation.

5. Number of Subjects

Up to 75 subjects seeking prenatal care at the University of New Mexico will be enrolled. Subjects will be pregnant, age 18 years or older, and registered as outpatients. Pregnant women are included because the purpose of this study is to determine the feasibility of studying the use of an oral probiotic agent in healthy, low risk, GBS positive pregnant women at term. We also propose to explore the effect of the probiotic on maternal GI symptoms and identify significant barriers to probiotic use in our population. Other special classes of subjects such as children, prisoners, and institutionalized individuals will not be enrolled.

This includes low risk patients seeking prenatal care at the University of New Mexico. Approximately 1500 women received prenatal care in the UNM Midwifery and OBGYN clinics in 2019 and approximately 20% were colonized with GBS. This gives us an adequate population from which to draw our study sample. We anticipate screening approximately 150 subjects over 8 months to allow us to enroll up to 75 subjects for our study after screening failures. A 30% dropout rate has been incorporated into sample size estimation to account for development of risk factors or failure to follow study procedures. These estimates are derived from Marquette University's randomized control trial pilot study of probiotics in pregnancy conducted at Marquette University and their current NIH funded double-blind randomized-controlled trial of Florajen3 to reduce GBS antenatal colonization. Tricore Lab has verified a 20% positive rate of GBS in our prenatal study population. For this open-label randomized control trial and feasibility study, a total sample of up to 75 participants will be targeted for enrollment and will be randomized to either the intervention group (receiving probiotics) or routine care (no intervention). A 30% dropout rate is assumed based on a preliminary study conducted at Marquette University; therefore, we anticipate that approximately 50 participants will

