Any participant may withdraw from the study at any time without penalty and will continue to receive the clinical standard of care. Data collected until that point will remain in the study database and may be used for data analysis. A subject may be withdrawn from the study without her consent at the discretion of the midwife and study staff if they believe she no longer meets study inclusion criteria or if she meets exclusion criteria, or if they believe that it is not in her best interest to continue study participation.

Page 19 of 31 Version Date: 12/2/2021

Investigators may withdraw a subject if the subject is not following the study protocol. If a woman is withdrawn from the study either at her own discretion or that of the research staff, she may continue with the standard of care performed in the usual fashion.

To minimize withdrawal from the study, patients will be enrolled and randomized only after confirmation of meeting eligibility criteria. According to the 2010 CONSORT guidelines, we will analyze all participants assessed for eligibility within the study. We will document and report eligibility criteria not met or reasons for declining participation in the study. We will also document reasons for withdrawal from the study if the patient has been enrolled and later revokes consent to participate in the study. The withdrawal procedure is clearly documented in the study consent.

16.Data Management/Confidentiality

A limited data set of data will be shared with Marquette University per the Data Use Agreement in place. Subject ID will be assigned based on order of enrollment in the study. Randomization assignment will be generated by a computer based randomization table and assigned by a research coordinator. Assignments will be made through the REDCap database. All data collection sheets and questionnaires will contain the subject number and day of the clinic visit. PHI including patient name, date of birth, phone number, and medical record number will need to be collected to track for appointments. No other patient identifiers will be collected aside from those listed above.

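### Unblinded staff may withdraw a randomised woman before her labour-admission swab, and the plan defines no as-randomised analysis set to contain the effect

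*Combined protocol and SAP*

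**What the plan says.** Section 15 of the combined protocol and SAP gives staff two relevant grounds for ending a woman's participation.

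- Conduct: "Investigators may withdraw a subject if the subject is not following the study protocol".
- Eligibility: "A subject may be withdrawn from the study without her consent at the discretion of the midwife and study staff". The trigger on this ground is a belief held by those staff, worded as "if they believe she no longer meets study inclusion criteria or if she meets exclusion criteria".

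A third ground, her best interest, is not questioned here. All of these are withdrawals from the study, not only from the capsules, and none is tied to a time point. A withdrawn woman goes on with standard care. On her data the section says: "Data collected until that point will remain in the study database and may be used for data analysis".

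The only statement about who is analysed is that "we will analyze all participants assessed for eligibility within the study". On reasons, the section says: "We will also document reasons for withdrawal from the study if the patient has been enrolled and later revokes consent". It makes no matching promise for withdrawals that staff initiate.

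Section 5 says: "A 30% dropout rate has been incorporated into sample size estimation to account for development of risk factors or failure to follow study procedures".

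Section 6 states that investigators, research staff and prenatal providers are not blinded. Its schedule has one GBS swab after randomisation, at T2 (labour admission). Section 7 makes that result the primary outcome, and section 12 says the swab is not standard of care. Section 13 specifies logistic regression for it, without naming an analysis set or a rule for missing T2 results.

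**The concern.** Whether a randomised woman contributes to the primary comparison can depend on a judgement made after randomisation by someone who knows her group. Because the T2 swab is done only for research, a withdrawal before labour would ordinarily remove her primary outcome.

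The loss need not be balanced between arms. Only probiotic women have capsules to miss. A control woman could start an over-the-counter probiotic, which is an exclusion criterion in section 4. A complication arising after randomisation could be read as an exclusion in either arm.

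Two further things are at stake. Nothing in the documents says the adverse event forms at T3 to T5 continue after a staff withdrawal, so secondary outcomes may be lost for the same women. Removing non-adherent women would also discard adherence information that this feasibility study sets out to collect.

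**Working it through.** **The plan's own figure.** Section 5 enrols up to 75 women and assumes 30% dropout: 75 × (1 − 0.30) = 52.5, against a stated completion of about 50. The two agree at the document's rounding. The causes named for the 30% closely match the conduct and eligibility grounds in section 15. The figure is not split by cause, by arm or by who initiates, so it supplies no staff-withdrawal rate.

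**The text, step by step.**

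1. Section 15 ends study participation on either ground, at any time.
2. The woman then has standard care, and section 12 places the T2 swab outside standard care.
3. Data collected before withdrawal cannot include a T2 swab if she is withdrawn before labour.
4. The group assessed for eligibility is about 150 women (section 5). It includes women with no arm and no T2 swab, so it cannot serve as the set for a randomised comparison.
5. Section 13 does not supply another set.

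**Illustration of size.** Assumptions, none of them stated as plan values:

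- 1:1 allocation, 38 probiotic and 37 control;
- no true effect;
- clearance c = 0.18 in both arms (9/50 in the placebo arm of a trial cited in section 2), so 82% positive at T2.

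Let k probiotic women be withdrawn before T2, w = k/38, and let r be clearance in withdrawn women divided by clearance in retained women (R). Then c = (1 − w)R + w·r·R, so R = c / ((1 − w) + w·r). The spurious difference in percent positive, probiotic minus control, is c − R. Example, k = 4 and r = 0: R = 0.18 / (34/38) = 0.2012, a difference of −2.12 points.

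| r | k = 1 | k = 4 | k = 11 |
|---|---|---|---|
| 1 (unrelated to clearance) | 0 | 0 | 0 |
| 0.5 | −0.24 | −1.00 (OR 0.94) | −3.05 (OR 0.82) |
| 0 | −0.49 | −2.12 (OR 0.87) | −7.33 (OR 0.65) |
| 1.5 | +0.23 | +0.90 (OR 1.06) | +2.28 (OR 1.18) |

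The k = 11 column is an extreme case: it treats the whole 30% as staff withdrawals and puts them in the probiotic arm only. If control women are withdrawn instead (w = k/37, r = 1.5), the difference is −0.24 for k = 1 and −0.92 for k = 4.

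**Rejection rate with no true effect.** By exact enumeration of a two-sided 5% chi-square test:

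- all 75 observed: 5.2%;
- k = 4: 5.4% (r = 0.5) and about 6.0% (r = 0), against about 5.25% for the same 34 and 37 women with no selection;
- k = 11: 5.8% (r = 0.5) and 10.0% (r = 0).

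**Sampling error for scale.** At 26 swabs per arm the 95% half-width is 1.96 × √(2 × 0.82 × 0.18 / 26) = 20.9 points.

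**Best/worst-case range.** The width is k1/38 + k0/37, where k1 and k0 are the missing swabs in the probiotic and control arms. One missing swab adds 2.6 points (probiotic) or 2.7 points (control).

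- Four missing per arm: 28/38 − 31/37 = −10.1 to 32/38 − 27/37 = +11.2, a width of 21.3 points.
- Missing 12 and 11: 21/38 − 32/37 = −31.2 to 33/38 − 21/37 = +30.1, a width of 61.3 points. This describes dropout of any kind, not this clause.

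**The case against.** The strongest reply is that the harm is inferred and small.

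- **Loss of the swab is inferred.** Section 15 says staff may withdraw a woman, and no sentence forbids a later swab. That is so. But the swab is research-only and she reverts to standard care, so losing it is the natural reading.
- **Capsule non-adherence is not measured before T2.** The count is at T3, so earlier withdrawal for missed capsules would rest on informal knowledge. This stands and weakens that route, but the eligibility ground needs no count.
- **Some section 4 criteria apply only at entry.** Gestational age, and hypertension diagnosed before enrolment, are examples. This narrows the eligibility ground. Section 5 still counts newly developed risk factors among its causes of dropout. One missed prenatal visit is not a clear ground, because the inclusion list tolerates it and the exclusion list bars it.
- **Safeguards exist.** The plan says "patients will be enrolled and randomized only after confirmation of meeting eligibility criteria", and earlier data are kept. Both help, but neither can supply a T2 swab for a woman withdrawn later.
- **Reasons and follow-up may be covered elsewhere.** A summary form is kept on every participant, and section 15 refers to a withdrawal procedure in the consent form. The content of neither was available for this review, so this remains open.
- **The section 13 model, run on women with a result, is already close to an as-assigned analysis.** True in part. But section 15 names a different group, and section 13 lists adherence among possible covariates although it is measured only in the probiotic arm.
- **The shift is minor at plausible counts.** Agreed. No document supports a particular k or r.

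**Conclusion.** The concern holds as a defect in the plan's wording, and confidence in that is high. The withdrawal rule allows unblinded, post-randomisation exclusions that would ordinarily cost the primary outcome, and no stated analysis set or missing-swab rule limits the effect.

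No actual bias is shown, and its frequency and direction are not established. Under the stated assumptions, 1 to 4 probiotic-arm withdrawals shift the difference by between −2.1 and +0.9 points, well inside sampling error. The −7.3-point case requires 11 of 38 probiotic women to be withdrawn by staff, none of whom would have cleared, and no control withdrawals.

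This should be fixed: the correction is cheap, and lost swabs cannot be recovered after delivery.

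**What to change.** 1. State in section 15 that non-adherence, or an eligibility change after randomisation, does not by itself end outcome follow-up. Leave consent withdrawal, best-interest decisions and all clinical decisions, including those about the capsules, as they are.
2. Collect the T2 swab where there is a labour admission, and the T3 to T5 forms, from every randomised woman who still consents and has not been withdrawn on best-interest grounds.
3. Replace the sentence on women assessed for eligibility. The flow diagram reports everyone assessed; the primary analysis includes all randomised women with a T2 swab, in the group assigned.
4. Do not adjust that analysis for adherence.
5. Record the reason and timing of every withdrawal by arm, including staff-initiated and best-interest ones.
6. Report missing T2 swabs by arm, with a best/worst-case sensitivity analysis, since the primary set still requires a swab.
7. Reconcile the two section 4 lines on missed prenatal visits.

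**Cost.** Protocol wording, the IRB approval that section 14 requires for modifications, and probably matching consent text. Section 22 already lists one study swab per participant; the total number funded is not given. Non-adherence will dilute the estimate somewhat, and the sensitivity bounds will be wide and may show only that the result is fragile.
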